## List of Substantial Changes

The proposed revisions to the Version 1 of the Statistical Analysis Plan (SAP) dated 28 September 2016 and the rationale for these changes are summarised below.

SAP SECTION	REVISION	RATIONALE FOR REVISION
SAP Version 2 dated 10 September 2018		
General	REVISIONS MADE THROUGHOUT THE DOCUMENT: Protocol No. CSL627_3001 Amendment 2, 05 June 2015 REVISED TO Protocol No. CSL627_3001 Amendment 3, 27 January 2017.	To reflect the current protocol amendment.
Section 2.1 and 2.2 and accordingly throughout the document	Incidence of inhibitor formation to FVIII in Arm 2, PUPs was stated that would be performed on at least 50 PUPs. This condition has been removed.	Given that patients that develop inhibitors may be withdrawn from the study early, they would not necessarily achieve 50 exposure days. Therefore the text was adjusted to properly report the endpoint regardless of these circumstances.
Section 3.5.3	Efficacy Population definition has been changed removing the exclusive inclusion of subjects who do not have an inhibitor at any time point during the study.	Analysis by inhibitor status for PUPs will be included as a separate population and analysis.
Section 3.5.6	Region subgroups and Japanese subgroup added. Race subgroups added for inhibitors analysis.	To assess safety of CSL627 on regional and racial basis.
Section 3.5.6	Age subgroup changed to be based on age in this study.	To focus on age distribution in this study.
Section 4.1 and accordingly throughout the document	For PUPs, analyses of ABR, hemostatic efficacy, TEAE and IR will be presented overall and by inhibitor status.. Periods during which the subject receives injections for reasons different than prophylaxis are excluded.	To exclude periods in which other types of infusions might affect prophylaxis compliance.

Section 4.5.5	It has been specified that if a subject has two dose regimens on the same day, the frequency of the regimen will be summed and the doses will be averaged.	To handle mixed regimen assignment.
Section 4.5.7	Shift analysis in the current study from initial to final regimen has been added.	For completeness of analysis.

Section 4.5.3	Analysis of extent of exposure to rVIII-SingleChain has been stated to be also on Surgery population.	For consistency with Section 4.1.
Section 4.6.1.1	In the last bullet point, ABR analysis by final and initial prophylaxis regimen has been replaced with analysis within prophylaxis regimen.	For consistency throughout the section.
Section 4.6.3.1	Analysis of number of bleeding episodes over time has been removed.	No further need of this analysis.
Section 4.7.1	Analysis of Factor VIII inhibitor test results by Total EDs and EDs in the current study has been deleted for PTPs.  Analysis of time to inhibitor occurrence has been changed to consider number of EDs rather than time in months. Cumulative Incidence Curve presented rather than KM curve.	No further need of this analysis.  To focus on actual days of exposure.
Section 4.7.2	Summary table of all TEAEs occurred during the study and substudies including all PTPs and PUPs has been deleted.	No further need of this analysis.
Section 4.7.2.2	Positive test result for inhibitors performed at local laboratory removed from Medical events of SI	To include back due possible site differences in

		implementing the standardized methods.
Section 4.4, 4.7.1, 4.7.2.2 and 5.1	Minor typo errors have been edited.	NA
Header and signature pages	Company and contact details updated	
Interim analysis section	PTP CSR completed on Nov 2019	
General	
REVISIONS MADE THROUGHOUT THE DOCUMENT:
 
Protocol No. CSL627_3001 Amendment 3, 27 January 2017
 
REVISED TO
 
Protocol No. CSL627_3001 Amendments 4, 01 October 2019 & Amendments 5, 26 May 2020.
	To reflect the latest protocol amendments.
Section 4.1.2	Section added to summarize all sections impacted by Covid-19 amendment	To summarize contingency Covid-19 amendment.

## 1 Introduction

This document presents the Statistical Analysis Plan (SAP) for CSL Behring GmbH, Protocol No. CSL627\_3001: A Phase III Open Label, Multicenter, Extension Study to Assess the Safety and Efficacy of Recombinant Coagulation Factor VIII (rVIII-SingleChain, CSL627) in Subjects with Severe Hemophilia A.

The analyses to be conducted for the final complete Clinical Study Report (CSR) are described.

This SAP is based on the Clinical Study Protocol Amendment 5 dated 26 May 2020. The contingency amendment for Covid-19 dated from 18 June 2020 has been also included.

This SAP is based on the CRF Final Version 8 dated 03May2017.

This SAP provides additional details, e.g., data handling conventions, reporting conventions, and key data derivations.

## 2 Study Objectives

The objectives and endpoints as stated in the Clinical Study Protocol (CSP) Amendment 5 dated 26 May 2020 are presented below. Eligible subjects are males who have been diagnosed with severe hemophilia A (FVIII activity levels < 1%). There are 3 treatment arms in this study:

- Arm 1 (Previously Treated Patients [PTPs]): subjects of all ages who participated in a previous CSL-sponsored study with rVIII-SingleChain.
- Arm 2 (Previously Untreated Patients [PUPs]): subjects 0 to < 18 years of age who have not been exposed to any FVIII product (except for short-term use of blood products).
- Arm 3 (PTPs): subjects < 65 years of age with at least 50 exposure days (EDs) to any FVIII product and not currently enrolled in an rVIII-SingleChain study.

Arm 2 PUPs can enter this study either at the time of their first bleeding episode or previously diagnosed with hemophilia A in a non-bleeding state.

A surgery substudy (open to all study arms) will investigate the use of rVIII-SingleChain in surgery. CCI

Overall, the study objectives in all 3 study arms are to gain additional safety information on the incidence of FVIII inhibitors (including in PUPs), frequency of adverse events (AEs), and serious AEs (SAEs) associated with the use of rVIII-SingleChain, and to gain additional information on the efficacy of rVIII-SingleChain in PTPs and PUPs with severe hemophilia A. This study will collect information on subjects undergoing surgery during the study, thereby providing information on the safety and efficacy of rVIII-SingleChain during surgery.

The primary objectives of the study are:

In **Arms 1 and 3 (PTPs)**, the primary objective is

- To characterize the long-term safety profile of rVIII-SingleChain with respect to inhibitor development in PTPs.

In **Arm 2 (PUPs)** the primary objectives are:

- To characterize the safety with respect to inhibitor development in PUPs.
- To evaluate the efficacy of on-demand and prophylaxis treatment of rVIII-SingleChain in PUPs.

In **Arms 1 and 3 (PTPs)**, the secondary objectives are:

- To characterize the safety profile of rVIII-SingleChain with respect to inhibitor development after 10 EDs and after 50 EDs.
- To characterize the safety profile of rVIII-SingleChain with respect to antibodies against rVIII-SingleChain, and antibodies to Chinese Hamster Ovary (CHO) proteins.
- To collect and evaluate efficacy information on the prophylaxis and treatment of bleeding episodes.
- To assess the hemostatic efficacy of rVIII-SingleChain for PTPs who undergo surgery, using the 4-point evaluation of surgical treatment scale.

In **Arm 2 (PUPs)** the secondary objectives are:

- To further characterize the safety profile of rVIII-SingleChain with respect to inhibitor development.
- To characterize the safety profile of rVIII-SingleChain with respect to antibodies against rVIII-SingleChain, and antibodies to CHO proteins.
- To collect and evaluate the number of rVIII-SingleChain injections required for the treatment of bleeding episodes.
- To characterize consumption of rVIII-SingleChain in prophylaxis, on-demand treatment, and surgery.
- To assess the hemostatic efficacy of rVIII-SingleChain for PUPs who undergo surgery, using the 4-point efficacy evaluation of surgical treatment scale.
- To assess the occurrence of clinically significant abnormalities in vital signs after rVIII-SingleChain administration.

CCI

## 2.1 Primary Endpoint

In **Arms 1 and 3 (PTPs)**, the primary endpoint is:

- Incidence of inhibitor formation to FVIII in at least 200 PTPs with at least 100 EDs of rVIII-SingleChain.

In **Arm 2 (PUPs)** the primary endpoints are:

- Incidence of high-titer inhibitor formation to FVIII (i.e., inhibitor titer of  $\geq 5$  Bethesda units/mL during the study) in at least 50 PUPs
- Treatment success for major bleeding episodes, defined as a rating of “excellent” or “good” on the investigator’s clinical assessment of hemostatic efficacy 4-point scale.
- Annualized spontaneous bleeding rate (AsBR) during prophylaxis and on-demand treatment.

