Additional safety assessments include AEs, serious AEs (SAEs), laboratory values, physical examinations, vital signs, antibodies against rVIII-SingleChain and CHO proteins, and local tolerability (subject / caregiver assessment in all study arms, investigator assessment for site injections only in Arms 2 and 3). As part of the safety assessment, incremental recovery (IR) will be monitored.

CCI [REDACTED]

Pharmacokinetics In **Arms 1 and 3 (PTPs)**, IR will be assessed at Day 1 and at the closest visits after 10 EDs, after 50 EDs, and after 100 EDs (Arm 1: cumulative EDs from first dose of rVIII-SingleChain in the parent study; Arm 3: EDs from first dose of rVIII-SingleChain in the present study).

CCI [REDACTED]

Pharmacodynamics Not applicable.

Other Assessments Not applicable.

Statistical Analyses The incidence of inhibitor formation to FVIII over 100 EDs of rVIII-SingleChain in PTPs (Arm 1 and Arm 3) and the incidence of high-titer inhibitor formation over 50 EDs of rVIII-SingleChain in PUPs (Arm 2) will be reported together with two-sided 95% confidence intervals (CIs).

In Arm 2 (PUPs), treatment success of **major** bleeding episodes (defined as the percentage of bleeding episodes with a rating of "excellent" or "good" on the investigator's clinical assessment of hemostatic efficacy 4-point scale) will be reported together with a two-sided 95% CI. A generalized linear model will be used to account for within-subject correlation.

AsBR during prophylaxis and on-demand will be summarized using descriptive statistics. In addition, the number of spontaneous bleeding

episodes per year and associated 95% CI will be estimated based on a Poisson model.

Secondary and CCI endpoints will be summarized using descriptive statistics, or frequency counts and percentages. Descriptive statistics will include number of observations, mean, standard deviation, median, minimum and maximum; and additional descriptive statistics (eg, quartiles, coefficient of variation) may be reported when appropriate.

All data will be analyzed and presented separately for PTPs and PUPs as well as for the surgery and CCI substudies.

Interim Analyses

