2.1.2 Primary Endpoints

In **Arms 1 and 3 (PTPs)**, the primary endpoint is the incidence of inhibitor formation to FVIII in at least 200 PTPs with at least 100 EDs of rVIII-SingleChain.

In **Arm 2 (PUPs)**, the primary endpoints are:

- Incidence of high-titer inhibitor formation to FVIII (ie, inhibitor titer of ≥ 5 Bethesda units [BU]/mL) in PUPs with at least 50 EDs of rVIII-SingleChain.
- Treatment success for **major** bleeding episodes, defined as a rating of "excellent" or "good" on the investigator's clinical assessment of hemostatic efficacy 4-point scale.
- Annualized spontaneous bleeding rate (AsBR) during prophylaxis and on-demand treatment.

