11.3.3.1 Primary Safety Endpoint

In **Arms 1 and 3 (PTPs)**, the primary safety endpoint is the incidence of inhibitor formation to FVIII in at least 200 PTPs with at least 100 EDs of rVIII-SingleChain.

In **Arm 2 (PUPs)**, the primary safety endpoint is the incidence of high-titer inhibitor formation to FVIII in PUPs with at least 50 EDs of rVIII-SingleChain.

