#### 4.7.1 Incidence of Inhibitor Formation

The incidence of inhibitor formation to FVIII will be estimated for subjects in the Safety population who did not have inhibitors at baseline. Baseline assessments are defined as those assessments done before date and time or on the same date and time of the first dose. If time of inhibitors assessment or time of first dose is missing then the inhibitor result taken at the same date of the first dose will be considered as baseline. Inhibitor formation will be defined as any post-baseline inhibitor titer  $\geq 0.6$  BU/mL identified and confirmed by re-testing at a subsequent visit. Both tests must be performed by a central laboratory. A positive result not confirmed as positive by re-testing at a subsequent visit result will be considered as non positive. In the KM analysis of inhibitor occurrence, the first positive result will be considered as an event. A positive result not confirmed as positive by re-testing at a subsequent visit result will not be considered as an event. Positive FVIII inhibitors will be further categorized as low or high titer. Low-titer inhibitors are defined as positive inhibitors with a titer of  $\leq 5$  BU/mL. High-titer inhibitors are defined as positive inhibitors with a titer of  $> 5$  BU/mL.

For the inhibitor incidence after 10 Total EDs, the numerator will include all subjects with inhibitors observed at the closest visit up to 10 EDs ( $\leq 10$  EDs). The denominator will include all subjects with at least 10 EDs ( $\geq 10$  EDs) plus subjects with less than 10 EDs but with inhibitors.

- Numerators = Number of PTP subjects who develop inhibitors up to 10 EDs ( $\leq 10$  EDs)
- Denominators = Total number of PTPs with at least 10 EDs ( $\geq 10$  EDs) + subjects with less than 10 EDs with inhibitors. Subjects not tested at  $\leq 10$  EDs will be excluded.

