##### The Inhibitor incidence after 50 Total EDs

- Numerators = Number of PTP subjects who develop inhibitors up to 50 EDs ( $\leq 50$  EDs)
- Denominators = Total number of PTPs with at least 50 EDs ( $\geq 50$  EDs) + subjects with less than 50 EDs with inhibitors. Subjects not tested at  $\leq 50$  EDs will be excluded.

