##### The Inhibitor incidence after 100 Total EDs

- Numerators = Number of PTP subjects who develop inhibitors up to 100 EDs ( $\leq 100$  EDs)
- Denominators = Total number of PTPs with at least 100 EDs ( $\geq 100$  EDs) + subjects with less than 100 EDs with inhibitors. Subjects not tested at  $\leq 100$  EDs will be excluded.

CCI

Same algorithm will be applied for PUPs.

For PUPs incidence of transient inhibitors (negative results within 6 months after positive result) will be also provided.

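### Arm 2 primary safety endpoint: high titer is ≥5 BU/mL in the endpoint but >5 in SAP 4.7.1, the SAP states both 50 and 24 PUPs, and the visible SAP rule does not show the protocol's high-titer denominator

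*SAP*

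**What the plan says.** **Event cut.** Protocol 2.1.2 names the endpoint: "Incidence of high-titer inhibitor formation to FVIII (ie, inhibitor titer of ≥ 5 Bethesda units [BU]/mL"). SAP 2.1 and 2.2.2 use the same cut, and SAP 2.2.2 puts low titer at 0.6 up to, but not including, 5. SAP 4.7.1, which holds the inhibitor analysis, differs: "High-titer inhibitors are defined as positive inhibitors with a titer of" more than 5 BU/mL, with low titer at 5 or below. Protocol 8.6.1 has this second pair of cuts. The withdrawal texts in Protocol 4.2.1 and SAP 3.6 also use more than 5.

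**Size.** SAP 2.1 ends its definition "Bethesda units/mL during the study) in at least 50 PUPs". SAP 2.2.2, SAP 3.1 and the Planned Number of Subjects paragraph of SAP 3.9 repeat the 50. The Sample Size Estimation paragraph of SAP 3.9 gives at least 24 PUPs and 224 subjects in all. The protocol gives 24 in the synopsis and in 1.3, 3.5 and 11.1. SAP 4.11 reports that the 50-PUP condition was taken out. Protocol 11.1 and SAP 3.9 both credit the sample size to the 2011 EMA guideline.

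**Rule.** Protocol 11.3.3.1 states that "the primary safety endpoint is the incidence of high-titer inhibitor formation to FVIII in PUPs with at least 50 EDs of rVIII-SingleChain". Protocol 11.3.3.2(b) gives the denominator: PUPs with 50 or more exposure days (EDs), plus those short of 50 EDs who have a high-titer inhibitor. In SAP 4.7.1 the 50-ED numerator is "Number of PTP subjects who develop inhibitors up to 50 EDs". Its denominator is PTPs with at least 50 EDs plus "subjects with less than 50 EDs with inhibitors. Subjects not tested at" 50 EDs or earlier are left out. The SAP then adds "Same algorithm will be applied for PUPs". On the period covered, the protocol synopsis refers to "the incidence of high-titer inhibitor formation over 50 EDs of rVIII-SingleChain in PUPs (Arm 2"), while SAP 2.1 counts titers during the study.

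**The concern.** This is one of three Arm 2 primary endpoints and the one that carries the PUP safety question. With about 24 subjects, one reclassified event moves the incidence by about four points. The SAP should therefore hold one cut, one numerator, one denominator and one event window.

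As the text stands, two analysts could classify a titer of exactly 5 BU/mL differently. They could also disagree on whether a low-titer PUP who stops short of 50 EDs belongs in the denominator. The study is open-label, so any such choice left until the data are in view invites doubt about how it was made. The leftover 50 leaves the endpoint definition with a size that the study no longer plans.

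**Working it through.** **1. The plan's own total.** 200 PTPs + 24 PUPs = 224, as SAP 3.9 states. 200 + 50 = 250, which it does not state. The two PUP figures in SAP 3.9 cannot both be the current target. This conflict does not rest on SAP 4.11, which only shows that removal of the 50 was intended.

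**2. Attribution of the size.** Protocol 1.3 quotes the 2011 guideline as asking for a minimum of 50 PUPs. It then says that the guideline was updated in 2018 and that agreement was reached to stop enrolling. So 24 does not come from the 2011 text.

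**3. Event cut.** The two cuts differ only for a PUP whose highest titer is exactly 5 BU/mL. The effect of one such PUP is 1/24 = 4.2 points. Example with exact (Clopper-Pearson) 95% limits, the method in SAP 4.7.1:

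- Cut >5: 4/24 = 16.7% (4.7% to 37.4%)
- Cut ≥5: 5/24 = 20.8% (7.1% to 42.2%)

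**4. Denominator.** Let A be PUPs with at least 50 EDs, h high-titer PUPs below 50 EDs, and l low-titer PUPs below 50 EDs.

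- Protocol 11.3.3.2(b), high-titer numerator: h / (A + h)
- High-titer numerator on the visible SAP 4.7.1 denominator: h / (A + h + l)

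Assumptions: 24 PUPs; 8 with any inhibitor (Protocol 1.1 cites 35.4%, and 0.354 × 24 = 8.5, taken as 8); all 8 stay below 50 EDs; the other 16 reach 50 EDs. The documents give no high/low split, so h runs from 3 to 6.

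| h | Protocol rule | SAP denominator |
|---|---|---|
| 3 | 3/19 = 15.8% | 3/24 = 12.5% |
| 4 | 4/20 = 20.0% | 4/24 = 16.7% |
| 5 | 5/21 = 23.8% | 5/24 = 20.8% |
| 6 | 6/22 = 27.3% | 6/24 = 25.0% |

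The SAP denominator is lower by 2.3 to 3.3 points. This is the extreme case. If the low-titer PUPs reach 50 EDs, they enter A, l = 0, and both rules give h/24.

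**5. Untested-subject exclusion.** Protocol 11.3.3.2 has none. Dropping one event-free PUP moves 4/24 = 16.7% to 4/23 = 17.4%.

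**6. What the two sizes imply.** With zero events the upper limit is 1 − 0.025^(1/n): 14.2% at n=24 and 7.1% at n=50.

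**The case against.** The strongest reply concerns the rule. The 10-, 50- and 100-ED formulas in SAP 4.7.1 closely follow Protocol 11.3.3.4.1, the secondary rule for intermediate timepoints, and that section extends the rule to PUPs by inhibitor type. On this reading the carry-over sentence serves the secondary endpoints only. The primary rule then stands in Protocol 11.3.3.1 and 11.3.3.2, and nothing visible in SAP 4.11 withdraws it. Redacted text also sits directly beside the carry-over sentence and may contain the primary rule. This largely stands. It limits the point to the visible text and to moderate confidence. It does not explain ≥5 against >5, or 50 against 24.

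On the window, counting titers during the study may describe how a confirmed inhibitor is graded by its peak, rather than when it must arise. SAP 4.7.1 also reports PUP inhibitors by EDs at first positive test, with a category above 50, so late onset is not lost. This stands too. The wording needs reconciling, but a conflict of windows is not established.

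The untested exclusion would rarely apply, because Protocol 8.6.1 samples PUPs at every scheduled visit. It is still an addition that the protocol does not have.

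A reader might infer that the SAP would report any-inhibitor incidence, here 8/24 = 33.3%, as the primary result. The documents do not support that. Both call the endpoint high-titer, and SAP 4.7.1 splits positives by titer.

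**Conclusion.** The two wording conflicts are certain. The endpoint cut of ≥5 BU/mL disagrees with the >5 in SAP 4.7.1; the effect is 4.2 points per PUP peaking at exactly 5 BU/mL, at n=24, and nil otherwise. The SAP's 50 PUPs disagrees with its own 24 and 224 and with the protocol; the effect on the incidence is nil.

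A reader might infer that the second conflict misstates the trial's precision. It does not, because neither document states a precision and no sample size calculation was made.

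The rule gap holds with moderate confidence. The visible SAP text does not show the high-titer denominator of Protocol 11.3.3.2(b), and the effect is 2.3 to 3.3 points under the assumptions above, falling to zero if low-titer PUPs reach 50 EDs. The numerator sentence in Protocol 11.3.3.2 also does not itself say high-titer for PUPs, although its reference to 11.3.3.1 implies it.

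Overall this is a consistency correction worth making before database lock. It does not show that the primary analysis is invalid.

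**What to change.** For PUPs only, before database lock:

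- **SAP 4.7.1, cut.** For the endpoint analysis use the endpoint's own classes: high ≥5 BU/mL; low ≥0.6 to <5.
- **SAP 4.7.1, primary rule.** Write out Protocol 11.3.3.2(b). Numerator: PUPs with a confirmed high-titer inhibitor. Denominator: PUPs with at least 50 EDs plus PUPs with fewer than 50 EDs and a high-titer inhibitor. Leave out the untested-subject exclusion here. Keep the 10- and 50-ED algorithm for the secondary endpoints.
- **Window.** State one ED window for events, reconciling SAP 2.1, SAP 4.7.1 and the protocol synopsis. Say whether the during-the-study wording grades the peak titer or sets the period for onset.
- **Protocol 11.3.3.2.** Make the numerator say high-titer for PUPs.
- **Size.** Replace 50 by 24 PUPs in SAP 2.1, 2.2.2, 3.1 and 3.9, and update SAP 4.11. In Protocol 11.1 and SAP 3.9, stop crediting the 24 to the 2011 guideline.
- **Other passages with >5.** Protocol 4.2.1 and 8.6.1 and SAP 3.6 must be reconciled with the endpoint by the sponsor. No clinical value is proposed here.

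The cost is wording in these sections. It needs no new data or subjects, and the completed PTP analysis is unchanged.

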## 2.2 Secondary Endpoints

### 2.2.1 Secondary Efficacy Endpoints

In **Arm 1 and Arm 3 (PTPs)**, the secondary efficacy endpoints are:

- Annualized bleeding rate (ABR) (traumatic and non-traumatic) during prophylaxis and on-demand treatment.
- Treatment success for all bleeding (major and minor) episodes defined as a rating of “excellent” or “good” on the investigator’s clinical assessment of hemostatic efficacy 4-point scale.
- Percentage of bleeding episodes requiring 1, 2, 3, or > 3 injections of rVIII-SingleChain to achieve hemostasis.
- Mean actual dose per kg per subject per year; consumption of rVIII-SingleChain, expressed as number of injections and IU/kg per month and per year, as well as IU/kg per event (prophylaxis, on-demand and surgery).
- Treatment success for surgery, using the 4-point efficacy evaluation of surgical treatment scale.

In **Arm 2 (PUPs)**, the secondary endpoints are:

- Treatment success for non-major bleeding episodes, defined as a rating of “excellent” or “good” on the investigator’s clinical assessment of hemostatic efficacy 4-point scale.
- Percentage of bleeding episodes requiring 1, 2, 3 or > 3 injections of rVIII-SingleChain to achieve hemostasis.
- Annualized Bleeding Rate (ABR) during prophylaxis and on-demand treatment.
- Mean and actual dose per kg per subject per year; consumption of rVIII-SingleChain, expressed as number of injections and IU/kg per month and per year, as well as IU/kg per event (prophylaxis, on-demand, and surgery).
- Treatment success for surgery, using the 4-point efficacy evaluation of surgical treatment scale. Success is defined as a rating of ‘excellent’ or ‘good’.

